#### 11.6 Immune Response Analyses

At all visits, blood will be collected for determination of the immune response in serum, i.e. anti-pTau and anti-Tau IgG and IgM, anti-ePHF IgG, anti-T50 IgG, anti-CRM IgG and anti-CpG IgG titers.

#### **11.6.1 Immune Response for Primary Endpoints**

Descriptive statistics of actual values and changes from baseline as outlined in section 11.0, with the addition of Geometric Mean and 95% normal approximation confidence intervals (CI) as outlined in sections 8.15 and 8.17, will be presented for the primary immune response variable, anti-pTau IgG and anti-ePHF IgG titers in serum by Visit [Baseline, Visit 2 (Week 2), Visit 3 (Week 8), Visit 4 (Week 10), Visit 4.1 (Week 15), Visit 4.2 (Week 20), Visit 5 (Week 24), Visit 6 (Week 26), Visit 6.1 (Week 31), Visit 7 (Week 36), Visit 7.1 (Week 42), Visit 8 (Week 48), Visit 9 (Week 50), Follow-up Visit 10 (Week 67) and Follow-up Visit 11 (Week 74)] and Treatment Group [TFL Shell Table 14.2.1.1, 14.2.1.1.1; 14.2.5.1, 14.2.5.1.1]. This variable will further be summarized by Treatment Group for responder rate [TFL Shell Table 14.2.1.2, 14.2.1.2.1; 14.2.5.2, 14.2.5.2.1], and area under the curve and peak [TFL Shell Table 14.2.1.3, 14.2.1.3.1; 14.2.5.3, 14.2.5.3.1] by Treatment Group (and overall for baseline data only) in the Intention-to-Treat Population.

The time-dependent development of the geometric mean titers will be displayed graphically per Treatment Group for the actual values as well as for change from baseline [TFL Shell Figure 14.1.1.1, 14.1.1.1.2; 14.1.5.1, 14.1.5.1.1, 14.1.5.1.2] and by subject [TFL Shell Figure 14.1.1.2, 14.1.5.2]. Boxplot of the actual value summarized by Visit and Treatment Group will also be prepared [TFL Shell Figure 14.1.1.4 and 14.1.5.4].

Response rates by Visit will be displayed graphically in a response rate verses dose plot to investigate whether there is any dose response relationship [TFL Shell Figure 14.1.1.3; 14.1.5.3].

No statistical testing has been planned for antibody responses.

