## 6.1 Sample Size Considerations

Antibody titer assessment: The preliminary assessment of the antibody response and of the safety/tolerability (comparison between sub-cohorts) will be performed based on the data of all randomized subjects (6 on ACI-35.030/JACI-35.054 and 2 on placebo per sub-cohort) based on the timepoints related to the different IAs that will be conducted during the study. The initial number of subjects in each sub-cohort is consistent with the customary sample size employed in this type of studies. It is expected to allow clinical judgement of safety and tolerability, and to get preliminary evidence of an acceptable immune response. This sample size is also anticipated to provide sufficient evidence to support the possible enrollment of up to 16 additional subjects in the sub-cohort(s) showing the most favorable antibody response profile(s) with the objective to confirm the initial results. The number of additional subjects to be enrolled will be determined based on the preliminary observed immunogenicity response rate in the subcohort(s), and on the potential gain in precision of the response rate estimate in the expanded sub-cohort(s), and will not exceed 16 (12 on ACI-35.030/JACI-35.054 and 4 on placebo per sub-cohort). In addition, all other immunogenicity endpoints available at the interim timepoint may be considered in the sample size re-estimation. This may include but is not limited to the observed variability of titers such as the Anti-pTau IgG and the Anti-e-PHF IgG.

In total, up to 24 subjects can be randomized to cohort 1, cohort 2 and cohort 3, respectively (not taking into account sub-cohort(s) expansion). Any randomized subject withdrawing before the 2nd injection for reasons other than safety may be replaced in the cohort.

For safety, if an AE occurs at the rate of 1% or 10%, then the chance of observing such an AE among 6 subjects receiving that dose of active treatment will be 6% or 47%, respectively. If no AE of a given type is observed in any of the 6 subjects at a given dose of active treatment, then with 80% (90%) confidence the true incidence of that type of AE at that dose is at most 24% (32%).

An expansion was done in sub-cohort 1.2 in which 17 additional subjects were recruited (for a total of 25 subject in the sub-cohort) to allow further assessment of safety and immunogenicity at that dose.

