# 7.0 Study Endpoints

## 7.1 Primary Endpoints

The primary focus of this study is the assessment of safety and tolerability of ACI-35.030 and JACI-35.054. Safety and tolerability will be assessed by examination of a number of endpoints:

- Adverse events
- Immediate and delayed reactogenicity (e.g. anaphylaxis, local and systemic reactogenicity, including immune-complex disease)
- Suicidal ideation as assessed by Columbia-Suicide Severity Rating Scale (C-SSRS)
- Behavior as assessed by Neuropsychiatric Inventory Scale (NPI)
- Cognitive and functional assessments (RBANS, CDR-SB)
- Vital signs
- Magnetic Resonance Imaging (MRI) imaging
- Electrocardiogram
- Routine hematology and biochemistry evaluation in blood and urine
- Evaluation of autoimmune antibodies including anti-DNA antibodies in blood
- Inflammatory markers in blood and CSF

The immune response (i.e. immunogenicity) will be assessed by:

• Anti-pTau IgG and Anti-ePHF IgG titers in serum (e.g. geometric mean, change from baseline, responder rate, peak and area under the curve)

**Note**: anti-pTau IgG means the antibody response generated against pathological Tau species. This umbrella denomination includes anti-pTau IgG and anti-ePHF IgG responses.

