## 8.16 Geometric Mean Titer

The Geometric Mean Titer (GMT) is calculated by taking the antilogarithm of the mean of the log10 transformed titers. Antibody titers BLQ will be imputed as outlined in Section 8.14.

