## 8.20 Area Under the Curve (AUC)

Area Under the Curve (AUC) (AU/mL\*h) of anti-pTau and anti-Tau in serum will be calculated by using the trapezoidal rule up to Week 50 as well as up to Week 74.

AUC will also be provided for all other immune response parameters including anti-ePHF IgG (high coating).

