## 8.21 Peak Concentration

Peak concentration (AU/mL) of immune response parameters is defined as the maximum concentration observed post dose.

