# 11.0 Statistical Methods

All analyses will use SAS® version 9.4 or higher. Descriptive summaries will be tabulated by treatment group (ACI 300µg, ACI 900µg, ACI 1800µg, JACI 15µg, JACI 60µg). Where applicable, all subjects from each main cohort will be summarized together (excluding immunogenicity and biomarker TFLs).

Categorical data will be presented using counts and percentages, with the number of subjects in each category as the denominator for percentages. Percentages will be rounded to one decimal place except 100% will be displayed without any decimal places and percentages will not be displayed for zero counts.

Continuous data will be summarized using the number of observations (n), mean, standard deviation (SD), median, first quartile, third quartile, minimum, and maximum. Minimum and maximum will be rounded to the precision of the original data. Mean and median will be rounded to 1 decimal place greater than the precision of the original data. The SD will be rounded to 2 decimal places greater than the precision of the original data, up to a maximum of 3 decimal places.

A sensitivity analysis may be carried out at the end of the study if the number of patients impacted by the COVID-19 pandemic is large (e.g. >10% missed injections due to COVID-19) and thought to be impacting the efficacy and safety endpoints. This sensitivity analysis may exclude the patients affected by the pandemic.

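### SAP 11.6.1 states a geometric mean and 95% CI for by-visit titers but not for AUC and peak, which are primary measures built from the same titers

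*SAP*

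**What the plan says.** SAP 7.1 lists peak and AUC among the primary immunogenicity measures for anti-pTau and anti-ePHF IgG: "titers in serum (e.g. geometric mean, change from baseline, responder rate, peak and area under the curve".

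SAP 11.6.1 gives the by-visit titers descriptive statistics "with the addition of Geometric Mean and 95% normal approximation confidence intervals (CI) as outlined in sections 8.15 and 8.17". The next sentence covers responder rate, then AUC and peak, and names no statistic for the last two: "and area under the curve and peak [TFL Shell Table 14.2.1.3, 14.2.1.3.1; 14.2.5.3, 14.2.5.3.1] by Treatment Group". Sections 11.6.2 and 11.6.3 present the other antibody titers in the same manner, so they inherit the arrangement.

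The definitions do not fill the gap. SAP 8.16 defines the geometric mean for titers: "The Geometric Mean Titer (GMT) is calculated by taking the antilogarithm of the mean of the log10 transformed titers". Under SAP 8.20, AUC "in serum will be calculated by using the trapezoidal rule up to Week 50 as well as up to Week 74", and under SAP 8.21 peak "is defined as the maximum concentration observed post dose"; neither sets a log scale. Protocol 5.3.6.2 says only that peak and AUC will be described and summarized per dose group.

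That leaves the general rule in SAP 11.0: "Continuous data will be summarized using the number of observations (n), mean, standard deviation (SD), median, first quartile, third quartile, minimum, and maximum".

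**The concern.** By adding the geometric mean, the SAP treats titers as data to be summarized on the log scale. AUC and peak come from those same titers, yet the text puts them back on the arithmetic scale and gives no reason. Elsewhere the SAP names the geometric mean where it wants one: for the antibody ratios (11.6.2) and for volumetric MRI (11.7.4).

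On right-skewed data the arithmetic mean of a small group follows its largest value. The initial groups are small: "6 on ACI-35.030/JACI-35.054 and 2 on placebo per sub-cohort". No test is planned for antibody responses, so the descriptive summaries are the evidence. Protocol 1.4 says the primary endpoints will be the basis for choosing the vaccine. At stake is whether the AUC and peak tables give a stable picture of the dose groups that can be read alongside the geometric mean titers, with an indication of uncertainty.

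**Working it through.** **The plan's own figures.** SAP 6.1 gives sample-size figures only for adverse events among 6 subjects, and they reproduce:
- Chance of at least one event: 1 − 0.99^6 = 5.9% and 1 − 0.90^6 = 46.9% (stated 6% and 47%).
- Upper limits after 0 of 6: 1 − 0.2^(1/6) = 23.5% and 1 − 0.1^(1/6) = 31.9% (stated 24% and 32%).

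Nothing comparable is given for AUC, peak or titer spread.

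**Step 1: one high responder.** Put n − 1 subjects at 1 unit and one at k.

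| n | k | arithmetic mean | geometric mean = k^(1/n) | median | share of total |
|---|---|---|---|---|---|
| 6 | 10 | (5+10)/6 = 2.50 | 1.47 | 1.00 | 10/15 = 67% |
| 6 | 50 | (5+50)/6 = 9.17 | 1.92 | 1.00 | 50/55 = 91% |
| 18 | 10 | (17+10)/18 = 1.50 | 1.14 | 1.00 | 10/27 = 37% |

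The arithmetic mean moves most and the median does not move at all.

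**Step 2: sampling stability at n = 6.** Assume log-normal values with natural-log SD s = 0.8, 1.0 or 1.5 (log10 SD 0.35, 0.43, 0.65).

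For geometric means there is a closed form. The log ratio of two identical groups has SE = s·√(2/6) = 0.462 / 0.577 / 0.866.
- Chance of a false difference above 2-fold = 2·[1 − Φ(ln 2 / SE)], with ln 2 / SE = 1.50 / 1.20 / 0.80. This gives 13% / 23% / 42%.
- Chance of the wrong ranking at a true 3-fold ratio = 1 − Φ(ln 3 / SE), with ln 3 / SE = 2.38 / 1.90 / 1.27. This gives 0.9% / 2.9% / 10.2%.

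The arithmetic mean and median need simulation (400,000 pairs of groups of 6).

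| s | 0.8 | 1.0 | 1.5 |
|---|---|---|---|
| False >2-fold, arithmetic mean | 18% | 30% | 52% |
| False >2-fold, geometric mean | 13% | 23% | 42% |
| False >2-fold, median | 19% | 29% | 49% |
| Wrong ranking at true 3-fold, arithmetic | 1.6% | 5.0% | 15.6% |
| Wrong ranking at true 3-fold, geometric | 0.9% | 2.9% | 10.2% |
| One subject supplies over half the group total | 11% | 24% | 50% |
| Arithmetic and geometric means disagree on which identical group is higher | 14% | 16% | 20% |

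**Step 3: unequal group sizes.** SAP 6.1 records that the 900 µg sub-cohort was expanded to 25 subjects. The active/placebo split is not stated there; a 3:1 ratio would give about 18 or 19 active. With 18 against 6 and no true difference, the median ratio of arithmetic means is 1.05 / 1.08 / 1.23. The larger group ranks higher in about 54% / 56% / 59% of trials, against 50% by chance.

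**The case against.** The strongest reply is that the planned reporting already protects the reader.

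- The section 11.0 default includes the median, quartiles, minimum and maximum, and in Step 1 the median does not move. A reader might infer that AUC and peak get nothing beyond a mean and SD. The SAP does not support that.
- Individual peak and AUC values for the primary antibodies are in Listing 16.2.12.3 at the interim and final analyses. By-visit geometric means, individual curves and box plots are also planned. With 6 subjects, a dominant responder would be visible.
- The sentence on AUC and peak follows directly on the geometric-mean sentence, and the shells for Tables 14.2.1.3 and 14.2.5.3 are in a separate document. A reader might infer that no geometric mean is planned. The text shows only that none is stated.
- No passage makes the arithmetic mean of AUC or peak a decision criterion. Expansion rests on the response rate and its precision, and other immunogenicity endpoints may be considered. This SAP version records that the 900 µg expansion is done and that sub-cohort 2.3 and Cohort 3 were not started.
- The main problem is n = 6, and geometric means of 6 still mislead often.

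All of this stands as a limit on the size of the concern. It does not remove it. The median resists one outlier, but under log-normal sampling at n = 6 it is about as variable as the arithmetic mean, and it has no interval. If the shells already hold a geometric mean, the SAP should say so.

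**Conclusion.** The point holds as a cheap improvement. By its text, the SAP gives two listed primary measures a summary without a log-scale mean or an interval, while the titers they are built from get both. In the four active groups planned at 6 (300 µg, 1800 µg, 15 µg and 60 µg), the arithmetic mean can be driven by one subject and is moderately less stable than the geometric mean. Using the geometric mean lowers false 2-fold differences by about 5 to 10 percentage points over the assumed range of spread.

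Two further readings go beyond the documents. A reader might take every active group to be a group of 6, but the 900 µg group was expanded. A reader might also expect that larger group to look clearly better by size alone, but the effect is small at the two lower SDs.

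The figures assume log-normal AUC and peak with natural-log SD 0.8 to 1.5. The documents give no spread, and AUC, which integrates over many visits, need not have the same spread as a single-visit titer. No test or sample size depends on this point.

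**What to change.** In SAP 11.6.1, and by reference in 11.6.2 and 11.6.3, state that AUC and peak (Tables 14.2.x.3 and 14.2.x.3.1) are also summarized by geometric mean with a 95% CI, calculated on log10 values and back-transformed. Name this as the main descriptive comparison between dose groups. Keep the median, quartiles and range. Check the table shells and bring them into line with the text.

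In the same edit, correct the cross-reference in 11.6.1: it points to section 8.15, on imputation of low biomarker values, where 8.16 defines the geometric mean.

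The cost is one or two extra rows per table. No new data are needed.

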3.5.2.12 Visit 6 [Week 26]

This visit can take place within a period of up to 2 days.

- AEs
- Concomitant medications (describe new and/or changes from the previous visit)
- Physical and neurological examination
- Vital signs
- Cognition: RBANS (form B)
- Clinical status: CDR, NPI, C-SSRS
- Blood sample collected for:
 - routine hematology and biochemistry evaluation, including CRP
 - antibody response components including for example anti-pTau and anti-Tau IgG and IgM titers
 - Inflammatory cytokines
 - AD biomarker assessment
 - T-Cell profile assessment
 - ANA and anti-dsDNA testing
- Lumbar puncture for cerebrospinal fluid sample (12 mL) for cell count, inflammatory markers and exploratory biomarker testing (note: blood for serum albumin should be taken and measured concomitantly)
- Routine urine evaluation
- Brain MRI
- ECG

Due to the Covid-19 pandemic, local travel restrictions in Finland effective as of 18 March 2020, and the need to preserve the safety of study participants, changes are made to the schedule of visits and procedures of sub-cohort 1.1 subjects:

- Given that the situation is not anticipated to be resolved to allow all procedures to be performed according to the protocol, Visit 6 will not be performed for any sub-cohort 1.1 subjects for whom the planned Visit 6 falls during the at-risk period.
- Instead, a remote visit will be performed in which the subject and caregiver are interviewed by telephone concerning any adverse events or changes in concomitant medications. Where possible, the CDR, NPI and C-SSRS scales will be administered during this interview. The remote visit will be performed at the initially planned Visit 6 date and according to the time-window defined in the Schedule of Assessments, i.e. at week 26 ± 2 days.
- This change is not applicable to the subject who had Visit 5 (week 24) procedures according to the protocol on 18 February 2020.

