3.5.2.14 Visit 7 [Week 36]

- AEs
- Concomitant medications (describe new and/or changes from the previous visit)
- Physical and neurological examination
- Vital signs
- Blood sample collected for:
 - routine hematology and biochemistry evaluation, including CRP
 - antibody response components including for example anti-pTau and anti-Tau IgG and IgM titers
 - Inflammatory cytokines
 - AD biomarker assessment
 - ANA and anti-dsDNA testing
- Routine urine evaluation

Due to the Covid-19 pandemic, local travel restrictions in Finland effective as of 18 March 2020, and the need to preserve the safety of study participants, changes are made to the schedule of visits and procedures of sub-cohort 1.1 subjects:

- In case the situation is anticipated to not be resolved to allow all procedures to be performed according to the protocol, Visit 7 will not be performed. The decision will be taken on a caseby-case basis depending whether the visit for a particular subject is falling during the at-risk period.
- Instead, a remote visit will be performed in which the subject and caregiver are interviewed by telephone concerning any adverse events or changes in concomitant medications. Where possible, the NPI and C-SSRS scales will be administered during this interview. The remote visit will be performed at the initially planned Visit 7 date and according to the timewindow defined in the Schedule of Assessments, i.e. at week 36 ± 3 days.

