3.5.2.16 Visit 8 [Week 48]

- Assessment of the subject's decisional capacity: MacCAT-CR interview (in the Netherlands)
- AEs
- Concomitant medications (describe new and/or changes from the previous visit)
- Physical and neurological examination
- Vital signs before the administration of study medication
- Blood sample collected prior to administration of study medication for:
 - routine hematology and biochemistry evaluation, including CRP
 - antibody response components including for example anti-pTau and anti-Tau IgG and IgM titers

coagulation indices assessment

Inflammatory cytokines

AD biomarker assessment

- ANA and anti-dsDNA testing
- Routine urine evaluation and urinary pregnancy test
- Administration of study medication
- 4-hour clinical observation:
 - Vital signs and observation of the injection site 1, 2 and 4 hours after the administration of study medication
 - Physical examination before discharge

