# 6.0 Study Design

This section reflects the language from Global Protocol Version 7.0 dated 22-Oct-2021. Country-specific changes to the design of the study and the schedule of assessments have been included in the respective protocol versions (V7.0 dated 04-Nov-2021 (UK specific version)).

This is a multicenter prospective placebo-controlled, double-blind and randomized study to assess treatment with Tau targeted vaccines versus placebo over 50 weeks (i.e. 12 months) in up to 216 subjects with early Alzheimer's Disease. For both cohorts 1 and 2, immunizations will be performed at months 0 (Week 0), 2 (Week 8), 6 (Week 24)\* and 12 (Week 48). Based on the safety and immunogenicity results the protocol may be amended to test additional regimens. The subjects will be enrolled in up to 3 Cohorts, each with up to 72 subjects, the actual number depending on the number of sub-cohorts studied and the number of sub-cohorts in which expansion is performed.

\* Due to the Covid-19 pandemic, local travel restrictions in Finland effective as of 18 March 2020, and the need to preserve the safety of study participants, modifications were made to the schedule of immunizations of sub-cohort 1.1 subjects who had not received the 3rd injection at month 6 already: immunizations at month 6 (week 24) were not performed in 7 of 8 sub-cohort 1.1 subjects for whom the planned Visit 5 did not allow all assessments to be done according to the protocol. In addition, Visits 5 (Week 24), 6 (Week 26) and 7 (Week 36) were replaced by remote visits in case these fell during the at-risk period (refer to protocol sections 3.5.2. 10, 3.5.2.11, 3.5.2.12 and 3.5.2.14).

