#### Sub-cohort 1.1 (8 subjects)

ACI-35.030 at 300  $\mu$ g/dose will be administered in 6 subjects and the placebo will be administered in 2 subjects. The safety and tolerability data after all subjects have received the second injection in sub-cohort 1.1 permit dose escalation after review by Data Safety Monitoring Board (DSMB).

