## 9.2 Intention-to-Treat

The intention-to-treat (ITT) population is defined as all randomized subjects who received at least one dose of the drug during the study, and will be used for presentation of primary, secondary and exploratory endpoints and for description of baseline characteristics.

The ITT population will be analyzed and presented according to the treatment arm in which the subject was randomized regardless of the number of injections that the subject actually received.

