## 12.0 Changes from the Analysis Planned in the Protocol

Due to the COVID-19 pandemic a notification of an Urgent Safety Measure (USM) for a change to protocol study procedures, effective immediately, was submitted to FIMEA on **01-Apr-2020** and Finnish EC (TUKIJA) on **03-Apr-2020**. A protocol amendment following the USM including the below changes was submitted to FIMEA on **17-Apr-2020** and TUKIJA on **24-Apr-2020**:

- Replacement of Visit 5 (Week 24) and Visit 6 (Week 26) by remote visits in 7 of 8 Sub-cohort 1.1 subjects. As a consequence, the third immunization, as well as procedures and assessments requiring the subjects to travel at Visit 5 (Week 24) and Visit 6 (Week 26) were cancelled.
- Cancellation of the third phone call (P3), usually performed 48-72 hours after the third immunization. This change is impacting 7 of 8 subjects who have not had their immunization at Visit 5 (Week 24) prior to the at-risk period.

Due to the changes presented above IA #2 Sub-cohort 1.1 at Week 50 will be executed as follows:

- Individual data (listings and individual figures) will not be presented for IA #2 Sub-cohort 1.1 Week 50.
- Aggregate data (summary tables and figures) will be provided for all timepoints (up to Week 50) except the timepoints where the visits were missed by 7 of 8 subjects in Sub-cohort 1.1 for which we will have only 1 value (i.e. Visit 5 Week 24 and Visit 6 Week 26).

Footnotes will be included to all outputs affected by the selection criteria as given below:

• Aggregate data outputs: "Note: Aggregate data is provided for all visits except those missed by 7 out of 8 subjects in Sub-cohort 1.1 (Visits 5 and 6)."

In certain cases, where subjects missed any visit or dropped out from the study, IA will be executed as follows:

[figure not shown]
- If there is a risk of unblinding individual data (listings and individual figures) will be presented only up until the missed visit or data for those subjects will not be included.
- Aggregate data (summary tables and figures) will be provided for all timepoints

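### From Week 36 on, and in peak and AUC, the 300 µg results reflect one fewer injection as well as a lower dose, and the final dose-response displays do not separate the two

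*SAP*

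**What the plan says.** The synopsis of the protocol gives a dose-response curve for safety and immunogenicity as the reason for escalating ACI-35.030 through 300, 900 and 1800 µg. For the primary antibody endpoint, SAP 11.6.1 states: "Response rates by Visit will be displayed graphically in a response rate verses dose plot to investigate whether there is any dose response relationship". The same section tabulates titers by visit, responder rate, peak and AUC by treatment group in the ITT population. Under SAP 9.2 that population is presented "according to the treatment arm in which the subject was randomized regardless of the number of injections that the subject actually received". Peak (SAP 8.21) is the largest post-dose value. AUC (SAP 8.20) is trapezoidal, to Week 50 and to Week 74.

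SAP 6.0 reports that "immunizations at month 6 (week 24) were not performed in 7 of 8 sub-cohort 1.1 subjects". In that sub-cohort, ACI-35.030 at 300 µg "will be administered in 6 subjects and the placebo will be administered in 2 subjects". Protocol 3.5.2.12 names one exception: "This change is not applicable to the subject who had Visit 5 (week 24) procedures according to the protocol on 18 February 2020". SAP 12.0 says that the third immunization was cancelled and describes no replacement. It leaves the affected visits out of the interim aggregates because these are timepoints "for which we will have only 1 value (i.e. Visit 5 Week 24 and Visit 6 Week 26". Whether Week 36 was done on site was decided case by case, "depending whether the visit for a particular subject is falling during the at-risk period" (Protocol 3.5.2.14). At Week 48 the order is "Blood sample collected prior to administration of study medication for" antibody testing, so that draw precedes the last injection (Protocol 3.5.2.16).

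**The concern.** Nearly all of the lowest dose group lost an injection after Week 10, and the final outputs still place that group on the dose axis beside 900 and 1800 µg with no separation. A lower late response at 300 µg could come from the dose, the missed injection, or both, and the planned displays cannot tell these apart. Injection number is not incidental in this programme. Protocol 1.1.5 and 1.2 explain that the second-generation vaccines were developed because the first-generation response was not boosted by later injections. Week 50, which Protocol 5.3.6.2 names for the geometric mean and change from baseline, is one of the affected visits.

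Peak and AUC have a second problem: the same subjects also lack the Week 24 and 26 samples, and SAP 8.20 and 8.21 give no rule for missing draws.

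**Working it through.** **1. How many active subjects missed the injection.** The plan's own count is reproduced: 8 subjects minus the one exception leaves 7. Let a be active and p placebo subjects who missed. Then a + p = 7 with a ≤ 6 and p ≤ 2, so a ≥ 5. Only (a, p) = (5, 2) or (6, 1) is possible. The arm of the exception is not stated.

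**2. Injections received before each sample** (schedule: Weeks 0, 8, 24 and 48; dosing-visit draws are pre-dose).

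| Sample | Missed Week 24 | As scheduled |
|---|---|---|
| Weeks 2 and 8 | 1 | 1 |
| Week 10 | 2 | 2 |
| Weeks 24 and 26 | no sample | 2 and 3 |
| Week 36 (if on site), Week 48 | 2 | 3 |
| Weeks 50, 67, 74 | 3 | 4 |

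Weeks 24 and 26 are a missing-data problem. The mixing of dose and injection number shows from Week 36.

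**3. Group average at 300 µg, assuming all other injections were given.** Before the Week 48 dose: (18 − 5)/6 = 2.17 or (18 − 6)/6 = 2.00, against 3. From Week 50: (24 − 5)/6 = 3.17 or (24 − 6)/6 = 3.00, against 4.

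**4. Samples behind peak and AUC.** This assumes that the later-added Week 15, 20, 31 and 42 draws were not taken in sub-cohort 1.1, which the documents do not state. Planned post-baseline draws are then Weeks 2, 8, 10, 24, 26, 36, 48 and 50 (8 to Week 50), plus 67 and 74 (10 to Week 74).
- Without Weeks 24 and 26: 2/8 = 25% and 2/10 = 20% of draws are lost.
- Without Week 36 as well: 3/8 = 37.5% and 3/10 = 30%.
- The trapezoid after Week 10 lengthens from 24 − 10 = 14 weeks to 36 − 10 = 26, or to 48 − 10 = 38.

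A maximum over fewer samples can only be equal or lower, so the sampling loss alone cannot raise the 300 µg peak. For AUC the direction is not fixed.

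**5. Weeks 24 and 26.** There is 0 or 1 active value. A rate from one subject has an exact 95% CI of 0–97.5% or 2.5–100%.

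**6. The exclusion analysis in SAP 11.0.** Removing affected patients leaves 6 − 5 = 1 or 6 − 6 = 0 active 300 µg subjects.

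**7. Illustration only; these assumptions are not in the documents.** Take no true dose effect, baseline 1, and a kth injection that adds a rise over two weeks to 10·b^(k−1), then decays with half-life h. Use b = 1, 1.5, 2 or 3 and h = 6, 12 or 20 weeks, with Week 36 sampled or not. The ratio of the reduced to the full schedule is 0.31–1.00 for peak, 0.39–1.07 for AUC to Week 50 and 0.34–1.04 for AUC to Week 74. A dose trend can thus appear without a dose effect. These ranges are not estimates for this trial.

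**The case against.** The plan is not silent. SAP 9.3 allows a per-protocol analysis by timepoint, which would keep 300 µg through Week 10 and drop affected subjects afterwards if the missed injection counted as a relevant deviation. SAP 11.6.1 already gives geometric means and response rates by dose at Week 10. The exposure table (14.1.6), the COVID-19 tables (14.1.1.3.2 and 14.1.1.3.3), the individual titer figures and the listings let a reader trace each missed injection. The table and figure shells are a separate document, so a footnote may exist there.

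All of this stands, and it rules out the inference that nothing planned bears on the problem. It does not close the gap. The per-timepoint analysis is optional, a missed injection is not among the listed per-protocol exclusions, and 9.3 itself says that missed administration might not be a major deviation. Traceability does not change the plotted comparison. SAP 12.0 adapts interim outputs only.

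A reader might also infer that dose selection was compromised. The documents do not support that: escalation and expansion could be decided from Week 10 data (SAP 10.4), which are unaffected, and sub-cohort 1.2 had already been expanded to 25. Nor do they show that 900 and 1800 µg were fully dosed. Protocol 3.1 allows further pandemic adjustments in Finland and other countries, so the contrast here is with the schedule.

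**Conclusion.** The point holds for the final ITT response-rate-versus-dose plots from Week 36 on, and for peak and AUC to Weeks 50 and 74. In these, 5 or 6 of the 6 active 300 µg subjects are one injection short of the schedule, so dose is mixed with injection number. Peak and AUC also lack the Week 24 and 26 samples. Displays through Week 10 are sound on this point.

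No antibody testing is planned, so no error rate or power changes; the harm is to the dose-response interpretation. Its size is unknown, and it would be wrong to read the lost draws as a percentage bias or to assume that AUC must be understated. The count is certain from the documents. The injection contrast assumes that the other injections were given as scheduled, and the draw counts assume no later-added visits in sub-cohort 1.1. This is an inexpensive improvement that should be made.

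**What to change.** In SAP 11.6.1, carried to 11.6.2 and to 11.6.3 where the assay applies to Cohort 1 (Appendix 3 marks anti-CRM as not applicable):

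1. Keep all ITT outputs. In the dose plots and the peak and AUC tables, mark 300 µg from Week 24 on as a reduced-injection group, giving n, injections received and missing samples. At Weeks 24 and 26 show n, or omit the point as Section 12.0 does for the interim analysis.
2. In 9.3, commit to the per-timepoint per-protocol analysis and class the missed Week 24 injection as a deviation affecting immunogenicity from that visit on.
3. Name the already planned Week 10 geometric mean titer and response rate as the three-dose comparison at equal injection number (two), and add peak and AUC through Week 10. Also show 300 µg at Week 50 beside 900 and 1800 µg at Week 26. Each is two weeks after the third injection, but state that the interval before that injection differs (48 − 8 = 40 weeks against 24 − 8 = 16).
4. State that late dose-response statements including 300 µg are confounded by injection number. Rest them on 900 versus 1800 µg only after checking the injections actually received in those groups.
5. In 11.0, state that the exclusion analysis is not informative for 300 µg.

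The cost is SAP wording and a few extra outputs from existing data. The Week 10 comparison is imprecise (3 of 6 responders has an exact 95% CI of 11.8–88.2%) and says nothing about later boosting, and late statements would rest on two doses.
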